8.8 Biospecimen Correlative Studies

As of protocol Amendment 7 Version 8, research samples will no longer be collected from subjects on treatment or active follow-up for correlative analyses.

8.8.1 Blood Samples for Correlative Studies

Blood (15mL) will be collected at each time-point for correlatives (characterization of immune cell subsets and flow cytometry) as outlined in the Study Calendar in Section 7. Comprehensive peripheral immune profiling techniques will be employed including:

- Soluble immune analytes measurements combining cytokine, chemokine and growth factor profiling [15 cytokines (IL-1b, IL-2, IL-3, IL-4, IL-5, IL-6, IL-7, IL-9, IL-12p70, IL-13, IL-15, IL-17, IL-22, TNF α , INF γ); 5 chemokines (IL-8, MIP1a, MIP1b, MCP1, IP10); and 5 growth factors (VEGF, FGF, PDGF, EGF, HGF) together with 3 markers of hypoxia and bone remodeling (IGF-1, HIF, RANK-L)].
- Flow cytometry-based enumeration and characterization of circulating effector and functional memory T cell mobilization (T helper and cytotoxic T cell subsets) [23] as well as $\gamma\delta$ T cells, NK cells, and inducible NK-T activation [23, 24].
- Circulating T cells ($\alpha\beta$ and $\gamma\delta$ subsets) clonal expansion assessment TCR-VD(J) rearrangement sequencing.
- Immunoseq[®] T cell clonal expansion measurement: DNA will be extracted from PBMCs for Immunoseq[®] sequencing of TCR's CRD3 region to be performed on a NGS Illumina[®] platform.

8.8.2 Blood Samples for Exploration of IRR

For subjects potentially experiencing grade ≥ 3 infusion-related adverse reaction (uniphasic or biphasic), we will conduct immune response analyses (with a particular emphasis on NK or T cell activation and polarization). In the event of a grade ≥ 3 IRR, every attempt will be made to draw a total of 15 mL of blood for immune response analyses, as soon as reasonably possible after the reaction if the subject is still in the infusion clinic.

8.8.3 Bone Marrow Samples

Bone marrow aspirates/biopsies will be collected at the time-points indicated in the Study Calendar in Section 7. In addition to routine clinical evaluation conducted on these samples (including flow cytometry, conventional cytogenetics and fluorescence in situ hybridization [FISH]), samples will also be evaluated for the following correlative studies:

- Flow cytometry-based tumor microenvironment analysis: MRD status will be assessed for this study in part using a flow cytometry-based MM MRD assay developed by the Euroflow consortium utilizing 10 markers (CD138, CD38, CD45, CD19 CD56, CD27, CD117, CD81, κ / λ free light chains) to identify plasma cells, differentiate normal from MM-PC and well as PC clonality. Using alternative gating strategy, this flow cytometry panel will also allow identification and characterization of NK, T, B and myeloid cell subsets.
- MRD assessment by NGS: MRD will be assessed via NGS which utilizes MM cell DNA from bone marrow samples.
- Micro-array / global gene expression analysis of isolated plasma cells.
- Clonal evolution of PC (and MM-PC subpopulation) IgG VJ rearrangement sequencing.

- Immunoseq[®] T cell clonal expansion measurement: DNA will be extracted from CD138- (plasma cell depleted) bone marrow fraction for Immunoseq[®] sequencing of TCR's CRD3 region to be performed on a NGS Illumina[®] platform.

In addition to the volumes required for routine clinical evaluation (if applicable), a minimum of 9mL of bone marrow aspirate (1st pull or 1st technical pull after needle repositioning) will be collected for MRD assessment by flow cytometry and NGS. An additional 10mL of bone marrow aspirate will be collected for CD138+ plasma cell isolation (B cell receptor sequencing).

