13. DISEASE EVALUATION

13.1 IMWG 2016 Response Criteria

Response	IMWG Criteria*
Abbreviations: NGF=next-generation flow. NGS=next-generation sequencing. FLC=free light chain. M-protein=myeloma protein. SPD=sum of the products of the maximal perpendicular diameters of measured lesions. CRAB features=calcium elevation, renal failure, anemia, lytic bone lesions. FCM=flow cytometry. SUVmax=maximum standardised uptake value. MFC=multiparameter flow cytometry. ¹⁸ F-FDG PET= ¹⁸ F-fluorodeoxyglucose PET. ASCT=autologous stem cell transplantation.	
IMWG MRD Criteria (Requires a complete response as defined below)	

Sustained MRD-negative	MRD negativity in the marrow (NGF or NGS, or both) and by imaging as defined below, confirmed minimum of 1 year apart. Subsequent evaluations can be used to further specify the duration of negativity (e.g., MRD-negative at 5 years)†
Flow MRD-negative	Absence of phenotypically aberrant clonal plasma cells by NGF‡ on bone marrow aspirates using the EuroFlow standard operation procedure for MRD detection in MM (or validated equivalent method) with a minimum sensitivity of 1 in 10 ⁵ nucleated cells or higher
Sequencing MRD-negative	Absence of clonal plasma cells by NGS on bone marrow aspirate in which presence of a clone is defined as less than two identical sequencing reads obtained after DNA sequencing of bone marrow aspirates using the LymphoSIGHT platform (or validated equivalent method) with a minimum sensitivity of 1 in 10 ⁵ nucleated cells § or higher
Imaging-positive MRD-negative	MRD negativity as defined by NGF or NGS plus disappearance of every area of increased tracer uptake found at baseline or a preceding PET/CT or decrease to less mediastinal blood pool SUV or decrease to less than that of surrounding normal tissue ¶
Standard IMWG Response Criteria ; NOTE: see [22, 30 & 31] for additional details	
Stringent Complete Response (sCR)	CR as defined below plus: 
 • normal FLC ratio ** and • absence of clonal cells in bone marrow by immunohistochemistry(κ/λ ratio ≤4:1 or ≥1:2 for κ and λ patients, respectively, after counting ≥100 plasma cells)††
Complete Response (CR)	
 • Negative immunofixation on the serum and urine ‡‡ and • disappearance of any soft tissue plasmacytomas and • < 5% plasma cells in bone marrow aspirates.

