
For MRD assessment, the first bone marrow aspirate should be sent to MRD (not for morphology) and this sample should be taken in one draw with a volume of minimally 2 mL (to obtain sufficient cells), but maximally 4–5 mL to avoid hemodilution.
 
*All response categories require two consecutive assessments made at any time before the institution of any new therapy; for MRD there is no need for two consecutive assessments, but information on MRD after each treatment stage is recommended (e.g. after induction, high-dose therapy/ASCT, consolidation, maintenance). MRD tests should be initiated only at the time of suspected complete response. All categories of response and MRD require no known evidence of progressive or new bone lesions or extra medullary plasmacytomas if radiographic studies were performed. However, radiographic studies are not required to satisfy these response requirements except for the requirement of FDG PET if imaging MRD-negative status is reported.
 
†Sustained MRD negativity when reported should also annotate the method used (e.g. sustained flow MRD-negative, sustained sequencing MRD-negative).
	

‡ Bone marrow MFC should follow NGF guidelines²⁶. The reference NGF method is an eight-colour two-tube approach, which has been extensively validated. The two-tube approach improves reliability, consistency, and sensitivity because of the acquisition of a greater number of cells. The eight-colour technology is widely available globally and the NGF method has already been adopted in many flow laboratories worldwide. The complete eight-colour method is most efficient using a lyophilised mixture of antibodies which reduces errors, time, and costs. 5 million cells should be assessed. The FCM method employed should have a sensitivity of detection of at least 1 in 10⁵ plasma cells.

§ DNA sequencing assay on bone marrow aspirate should use a validated assay such as LymphoSIGHT (Sequentia).

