14.5.5 Secondary Analysis

The frequencies and proportions of overall response will be calculated. Corresponding 95% confidence intervals will be estimated using the Clopper-Pearson method. OS, PFS, TTP, TTNT, and DoR endpoints will be analyzed using Kaplan Meier techniques. Selected landmarks will be estimated and reported. Logistic regression models and Cox proportional hazards models will be used to analyze the treatment response endpoints as functions of baseline subject and disease characteristics, and results from biomarker studies as previously described. The percent of subjects achieving MRD negative status will be summarized. Subgroup analyses will be conducted for selected efficacy endpoints on the subset of MRD negative subjects (i.e. time to event endpoints).

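### The MRD marrow volume in Section 8.8.3 conflicts with the MRD sampling rule in Section 13.1, and the sequencing definition of MRD negativity is inverted as written

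*Combined protocol and SAP*

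**What the plan says.** Section 8.8.3 (Bone Marrow Samples) states that, beyond routine clinical volumes, "a minimum of 9mL of bone marrow aspirate (1st pull or 1st technical pull after needle repositioning) will be collected for MRD assessment"; this volume serves both the flow and the NGS assay. It then adds a separate research volume: "An additional 10mL of bone marrow aspirate will be collected for CD138+ plasma cell isolation". It does not give the number of pulls, the volume per pull, or the split between the two MRD assays.

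The note to the response table in Section 13.1 says that "the first bone marrow aspirate should be sent to MRD (not for morphology") and asks for that specimen to be "taken in one draw with a volume of minimally 2 mL (to obtain sufficient cells), but maximally 4–5 mL to avoid hemodilution". For flow, the same notes say "5 million cells should be assessed" and ask for a sensitivity of at least 1 in 10^5.

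The sequencing row of that table defines MRD negativity as absence of clonal plasma cells, where "presence of a clone is defined as less than two identical sequencing reads".

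MRD is an exploratory objective (Section 2.4). In the analysis, "The percent of subjects achieving MRD negative status will be summarized" (Section 14.5.5), and time-to-event endpoints are examined in the MRD-negative subset. Section 8.8 and footnote 13 of the Study Calendar say that research sampling stopped with Amendment 7, Version 8.

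**The concern.** Two current parts of the protocol give sites different instructions for the same specimen: one sets a floor of 9 mL, the other a ceiling of 4–5 mL. The ceiling comes with its reason, which is hemodilution. Blood drawn with the marrow lowers the plasma-cell fraction, while the assay's detection limit stays where it is. If samples were diluted, some subjects with residual disease could be called negative. In a single-arm trial there is no concurrent arm in which such an error could cancel.

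The sequencing definition is a second problem with the same output. If it were applied as written, it would reverse every sequencing result. Section 14.5.5 does not say which assay decides MRD status, so a reversed rule could enter both the reported percentage and the MRD-negative subset.

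**Working it through.** **1. The two volumes.** Inputs: 9 mL minimum (Section 8.8.3); 2 mL minimum and 4–5 mL maximum, one draw, first aspirate (Section 13.1).

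- As a single draw: 9/5 = 1.8 and 9/4 = 2.25 times the ceiling.
- As several draws under a 5 mL ceiling: 9/5 rounds up to 2 pulls, 9/2 = 4.5 mL each.
- As several draws under a 4 mL ceiling: 9/4 rounds up to 3 pulls, 9/3 = 3 mL each.

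| Reading of Section 8.8.3 | At most 4–5 mL per draw | One draw | First aspirate |
|---|---|---|---|
| One pull of at least 9 mL | No | Yes | Yes |
| Two or three repositioned pulls | Yes | No | Only the first pull |

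Neither reading meets all three conditions for the whole 9 mL.

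**2. Direction and size of any error.** The plan gives no dilution factor, false-negative rate or positivity threshold, so this is an illustration only. From Section 13.1: 5 million cells assessed. Assumed: a true burden L, a marrow fraction f in the sample (1 = undiluted), and a minimum cluster of k cells for a positive call. The number of aberrant cells is taken as Poisson with mean 5,000,000 × L × f, so the chance of a false negative is P(X ≤ k − 1). For example, L = 10^-5 and f = 0.5 give a mean of 25, and P(X ≤ 19) = 0.134.

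| L | k | f = 1 | f = 0.75 | f = 0.5 |
|---|---|---|---|---|
| 1 × 10^-5 | 20 | 0.000 | 0.001 | 0.134 |
| 1 × 10^-5 | 50 | 0.481 | 0.971 | 1.000 |
| 2 × 10^-5 | 20 | 0.000 | 0.000 | 0.000 |
| 2 × 10^-5 | 50 | 0.000 | 0.001 | 0.481 |
| 5 × 10^-5 and 1 × 10^-4 | 20 or 50 | 0.000 | 0.000 | 0.000 |

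The false-negative chance never falls as f falls, so the direction is clear. The size runs from nothing to nearly every subject, depending on three quantities the documents do not supply. It is confined to burdens close to the detection limit.

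**3. The sequencing rule, read literally.**

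| Identical reads | Literal rule | Rule implied by the rest of the row |
|---|---|---|
| 0 or 1 | Clone present, so not negative | Clone absent, so negative |
| 2 or more | Clone absent, so negative | Clone present, so not negative |

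Every result changes sides: a sequencing-negative proportion p would be reported as 1 − p. This needs no assumption about dilution.

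**The case against.** The best defence of Section 8.8.3 is that 9 mL is a total for two assays, and that the mention of needle repositioning is itself a safeguard against hemodilution. Two draws of 4.5 mL, one per assay, would sit within 4–5 mL each. Section 13.1 also says should, not must, and does not say that flow and sequencing have to share one specimen. Much of this stands: a single 9 mL draw is not established. What does not stand is that the sections then agree. A second draw is not the first aspirate, and Section 8.8.3 never says that the volume is divided.

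On the sequencing row, the opening words make the intent clear, so the inversion is probably editorial. That is fair, but a classification rule should not depend on the reader reversing it.

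On importance, MRD is exploratory, is summarized without a test, presupposes a complete response in a 40-subject trial, and does not enter VGPR+. Research sampling has ended, so rewording Section 8.8.3 changes no future research sample. All of this stands and limits the weight of the point.

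**Conclusion.** The conflict between Sections 8.8.3 and 13.1 is real on either reading of the 9 mL, and the sequencing definition is wrong as written. Both bear on the MRD-negative percentage and the MRD-negative subset, and on nothing in the primary analysis.

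A reader might go further and infer that the planned sample biases the MRD-negative rate upward by a definite amount. For example, if residual disease is assumed to be uniform on a log scale from 10^-5 to 10^-2, with dilution of 1.3- to 2-fold, the misclassified share is log10(1.3)/3 = 3.8% to log10(2)/3 = 10.0% of true positives. The documents do not support that. They do not show that single 9 mL draws were taken, and they give neither the dilution nor the burden distribution. The calculation also treats 1 in 10^5 as a sharp cut-off, whereas Section 13.1 uses it as a floor on assay sensitivity. With an assumed 20-cell cluster, disease at 2 × 10^-5 diluted 2-fold is still detected almost always. Even at face value, an assumed 10 MRD-positive subjects in complete response would yield 0.4 to 1 misclassified.

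The supportable conclusion is narrower: any error runs toward false negatives, and its occurrence and size are unknown.

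**What to change.** 1. Correct the sequencing row in Section 13.1 so that fewer than two identical reads means absence of a clone and two or more means presence. Confirm that results already classified used that rule.
2. Reconcile Sections 8.8.3 and 13.1 by stating the number of pulls, the volume per pull, and which pull feeds flow and which feeds sequencing. Putting both assays on one 2 to 4–5 mL draw is not an obvious remedy, because it reduces the cells available to each and Section 13.1 sets its minimum to secure enough cells.
3. For samples already taken, report the MRD-negative rate and the MRD-negative subset with the sensitivity each assay achieved. Where pull order and volume per draw were recorded, add a sensitivity summary by draw volume. Where they were not, state a hemodilution caveat. Simply excluding samples above 5 mL is not advisable, since it could remove every single-pull sample that complied with Section 8.8.3.

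The cost is protocol wording and a minor extra summary, with no new procedure. The downside is that the MRD-negative rate carries a caveat and may look slightly less favourable.

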8.8.4 Storage of Biospecimens

Any specimens remaining after biospecimen-based studies are complete will be stored in the Atrium Health (AH) Immune Monitoring Core Laboratory for follow-up/validation studies.

9. DISCONTINUATION FROM TREATMENT AND STUDY WITHDRAWAL

9.1 Treatment Discontinuation Criteria

Study treatment will continue until one of the following criteria applies:

- Disease relapse or progression
- Intercurrent illness that prevents further administration of treatment
- Unacceptable adverse event(s)
- Subject decides to withdraw study consent
- General or specific changes in the subject's condition render the subject unacceptable for further treatment in the judgment of the investigator
- Study subject becomes pregnant

NOTE: In the event the criteria for the final analysis are met, and there are subjects who have not yet been discontinued from study treatment, they will continue to receive therapy until one of the above criteria applies.

9.2 Off Study

Subjects will remain on study until the criteria for the final analysis have been met.

Reasons a subject may be removed from the study early include, but are not limited to:

- Subject non-compliance with study participation, in the opinion of the investigator
- The subject or legal representative (such as a parent or legal guardian) withdraws study consent
- The subject is lost to follow-up
- Investigator's decision to withdraw the subject
- Subject death
- Early study termination

When subjects are removed from the study, the reason for study removal and date the subject was removed should be documented.

Subjects that are Off Study will not participate in any study related procedures, including data collection.

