8.7 Follow-up

For subjects who discontinue study treatment before relapse or PD, disease evaluations should continue to be performed until relapse or confirmed PD, death, start of a new anticancer treatment, withdrawal of consent to study participation, or until the criteria for the final analysis are met (Section 14.5.1) whichever occurs first. The schedule for disease evaluation should follow the schedule outlined during maintenance. Survival follow-up will occur every 3 months (+/- 30 days) from the last administration of protocol-directed therapy until death, lost to follow-up, or until the criteria for the final analysis are met (Section 14.5.1) and may be conducted via telephone. Any second primary malignancies discovered during long-term follow-up will be documented. Follow-up clinical information may also be obtained through chart reviews or other data sources (e.g. death registries).

The investigator is responsible for following the subject during the required follow-up period even if the subject lives elsewhere or has been released from his or her care and is being treated at another institution.

If the subject cannot be contacted following three attempted telephone calls over a period of 10 business days, the subject will be contacted in writing. Lost to follow-up is defined as four consecutive unsuccessful documented attempts (telephone and written) to contact the subject.

NOTE: in the event the criteria for the final analysis are met, and there are subjects who have not yet been discontinued from study treatment, subjects in follow-up will continue to be followed until all subjects have discontinued study treatment and completed the Safety Follow-up Visit (see above).

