14.3.4 Progression Free Survival

Progression free survival (PFS) is defined as the duration of time from enrollment to the study (treatment start date) to first occurrence of either PD or death. Disease progression must be objectively determined per IMWG 2016 criteria (see Section 13.1), where the date of progression is the date of the last assessment that identified PD. If the subject died without documented disease progression, the date of progression will be the date of death. For surviving subjects who do not have documented disease progression, PFS will be censored at the date of last disease assessment. For subjects who receive subsequent anti-cancer therapy prior to documented disease progression, PFS will be censored at the date of last disease assessment prior to the commencement of subsequent therapy. Subjects who have an initial PFS event immediately following 2 or more consecutive missed disease assessments will be censored at the date of the last assessment prior to those missed assessments. For participants with only one missed assessment, the documented PD status and assessment date will be used.

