14.5 Analysis Methods

14.5.1 Timing of Analysis

The primary analysis will occur after VGPR+ status (yes or no) has been determined for all subjects. Secondary endpoints will also be assessed at the time of the primary analyses. Updated analyses will be conducted after the PFS censoring rate reaches 20% or when all surviving subjects who are not lost to follow up or have not been withdrawn from the study have been on study for at least 3 years, whichever occurs first. A final analysis will be conducted after the overall survival censoring rate reaches 20% or after all surviving subjects who are not lost to follow up or have not been withdrawn from the study have been on study for at least 5 years, whichever occurs first.

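### Section 9.2 stops all data collection on subjects removed for non-compliance or by investigator decision, while 8.7 continues their follow-up; the conflict needlessly loses secondary PFS and OS data

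*Combined protocol and SAP*

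**What the plan says.** **Section 9.2 (Off Study).** The list of early removals is open: "Reasons a subject may be removed from the study early include, but are not limited to". Two entries rest on the investigator's judgement, with no criteria given: "Subject non-compliance with study participation, in the opinion of the investigator" and "Investigator's decision to withdraw the subject". A separate entry covers the subject or legal representative who "withdraws study consent", so the first two can apply to someone who still consents. The consequence is the same for every entry: "Subjects that are Off Study will not participate in any study related procedures, including data collection". The reason for and date of removal are to be documented.

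**Section 9.1** deals separately with stopping study treatment.

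**Section 8.7 (Follow-up).** Subjects who stop treatment before progression continue disease evaluations, and survival is followed every three months. The section adds: "The investigator is responsible for following the subject during the required follow-up period even if the subject lives elsewhere". It allows telephone contact and permits chart review and death registries. Footnote 6 to the Study Calendar (Section 7) is to the same effect.

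**Analysis.** Under 14.3.4, "For surviving subjects who do not have documented disease progression, PFS will be censored at the date of last disease assessment". Section 14.3.3 censors OS at the date the subject was last known to be alive. Section 14.5.5 uses Kaplan-Meier methods for both. The time-based conditions in 14.5.1 apply to "all surviving subjects who are not lost to follow up or have not been withdrawn from the study".

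**The concern.** Leaving treatment and leaving the study are different events, and the protocol mostly keeps them apart. Section 9.2 blurs the distinction by letting an investigator's judgement end data collection on a subject who has not asked for it to end. Vital status, and often progression status, would still be obtainable for such a subject.

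Kaplan-Meier estimation assumes that a censored subject has the same future risk as those still under observation. Removal by judgement is a setting in which that can fail, because the reasons for it may be related to how the subject is doing. PFS and OS for this four-drug regimen would then be misestimated through avoidable loss of data. Because 8.7 points the other way, sites could also handle identical cases differently.

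**Working it through.** **Step 1. The two sections side by side.**

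| Event | Ends disease evaluation (8.7) | Ends survival follow-up (8.7) | Ends all data collection (9.2) |
|---|---|---|---|
| Death | yes | yes | yes |
| Relapse or confirmed progression | yes | no | not listed |
| New anticancer treatment | yes | no | not listed |
| Withdrawal of consent | yes | not listed | yes |
| Loss to follow-up | not listed | yes | yes |
| Final-analysis criteria met | yes | yes | yes |
| Non-compliance, investigator's opinion | **not listed** | **not listed** | **yes** |
| Investigator's decision | **not listed** | **not listed** | **yes** |

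The last two rows are the conflict. Nothing in 8.7 limits it to subjects still on study, and nothing in 9.2 makes an exception for follow-up under 8.7. A subject in either row is owed follow-up by one section and barred from data collection by the other. Chart and registry review in 8.7 is permissive and is not stated to survive off-study status.

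**Step 2. What the analysis then does.** A removed subject without an event is censored under 14.3.3 and 14.3.4 and enters Kaplan-Meier as non-informatively censored. The plan has no sensitivity analysis for this.

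**Step 3. An illustration of size.** The plan states no figure to reproduce: PFS and OS have no event target, assumed dropout rate or hypothesis test.

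Input from the document: 24-month OS of 73.3% on KRd in the phase III trial (Section 1.2). Assumptions, none from the documents: exponential survival; a fraction f (10% or 15%) with h times the death hazard (2 or 3); all survivors in that fraction removed at month 6; 73.3% applying to the remaining subjects.

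Write S = 0.733, so that survival at month t is S^(t/24) for the remaining subjects and S^(ht/24) for the others.

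- True 36-month OS = (1-f)·S^1.5 + f·S^(1.5h)
- Kaplan-Meier limit = [(1-f)·S^0.25 + f·S^(0.25h)] × S^1.25, because only the lower-risk group is observed after month 6

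For f = 0.10 and h = 2:

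- True: 0.9 × 0.6276 + 0.1 × 0.3938 = 0.6042
- Kaplan-Meier: (0.9 × 0.9253 + 0.1 × 0.8562) × 0.6782 = 0.9184 × 0.6782 = 0.6229
- Overstatement: 0.0187

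| f | h | True 36-month OS | Kaplan-Meier | Overstatement (points) |
|---|---|---|---|---|
| 0.10 | 2 | 60.4% | 62.3% | 1.9 |
| 0.10 | 3 | 59.0% | 61.9% | 2.9 |
| 0.15 | 2 | 59.2% | 62.1% | 2.8 |
| 0.15 | 3 | 57.1% | 61.4% | 4.4 |

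(Overstatements are from unrounded values.) A simulation of 400,000 subjects under the same assumptions gives the same four overstatements. With h = 1 the two formulas coincide, so removal unrelated to prognosis causes no bias. With h = 0.5 and f = 0.10 the sign reverses: Kaplan-Meier 63.0% against a true 64.4%.

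**Step 4. Against sampling error.** With 40 subjects and OS near 60%, the standard error is about √(0.6 × 0.4 / 40) = 0.077, or 7.7 points. The illustrated bias is 1.9/7.7 = 0.25 to 4.4/7.7 = 0.57 of a standard error.

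**Step 5. The primary endpoint.** Under 14.4 the response-evaluable population is everyone who starts elotuzumab with measurable disease at baseline. Later removal does not take a subject out of that denominator.

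**The case against.** The strongest reply is that the subjects one would worry about most are already protected. Intercurrent illness, unacceptable adverse events and investigator-judged changes in condition are reasons for stopping treatment in 9.1, and 8.7 keeps those subjects in follow-up. What 9.2 adds is a residual group about whose prognosis the documents say nothing. PFS and OS are secondary and untested, and any plausible bias is small beside the sampling error. All of this stands. It limits the importance of the point but does not resolve the conflict of wording.

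Three stronger readings are tempting, and the documents do not support them.

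- *That 9.2 makes censoring informative and PFS and OS too favourable.* This is a risk, not a stated fact. Non-compliance could come from fitter subjects or from logistics, in which case the bias could be nil or negative, as Step 3 shows.
- *That the bias is large.* If 10% of subjects were each removed three months before an event that would have occurred by month 24, simulated 24-month PFS would read 60.2% against a true 53.1% (exponential, median 26.3 months). That scenario assumes removal tracks imminent events and is a constructed extreme.
- *That 14.5.1 is defective because it leaves withdrawn subjects out of its time-based conditions.* That is ordinary. Subjects no longer followed cannot accrue follow-up time, and the rule sets the timing of the analysis, not the estimates.

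**Conclusion.** The point holds as a contradiction between 9.2 and 8.7 with an avoidable loss of data. Consenting subjects can be removed by judgement, and 9.2 then discards follow-up that 8.7 requires and that would often be obtainable. Bias in the secondary PFS and OS estimates follows only if removal is related to prognosis, and the documents give neither the frequency of removal nor the prognosis of those removed. Under the stated assumptions the effect on 36-month OS is about 2 to 4 points, below one standard error for 40 subjects. The primary VGPR+ denominator is not touched. The change is still worth making: it costs little, and follow-up that was never collected may not be recoverable by the 3-year and 5-year analyses.

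**What to change.** Reconcile 9.2 with 8.7. State in 9.2 that data collection ends only on withdrawal of consent for follow-up, loss to follow-up, death, or study termination or final analysis (subject to the existing note in 8.7 on subjects still on treatment at that time). State that subjects removed for non-compliance or by investigator decision continue disease evaluation and survival follow-up under 8.7, including telephone contact, chart review and death registries. Leave the treatment-discontinuation criteria in 9.1 as they are; no treatment rule needs to change.

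Since 9.2 already requires the reason and date of each removal to be recorded, the number removed for each reason can be reported with the PFS and OS results.

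The cost is a wording amendment and a small amount of added follow-up work, using methods the protocol already provides.
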